5.6 Sample Size Determination

As part of an observational Registry, the target sample size of 1000 was not derived through a power driven hypothesis testing. Tables 1 & 2 below demonstrate the corresponding confidence interval length for estimated values for Registry Endpoints 1 and 2 at various sample size time points. The maximum sample size presented is 900 to allow up to 10% attrition rate.

Table 1: 30-Day Complication Free Rate Estimated Values & 95.0% Exact Conf. Interval

Estimated Value	Sample Size								
	100	200	300	400	500	600	700	800	900
90%	-7.6%/+5.1%	-5.0%/+3.8%	-4.0%/+3.2%	-3.4%/+2.8%	-3.0%/+2.5%	-2.7%/+2.3%	-2.5%/+2.1%	-2.3%/+2.0%	-2.1%/+1.9%
91%	-7.4%/+4.8%	-4.9%/+3.6%	-3.8%/+3.0%	-3.2%/+2.6%	-2.9%/+2.4%	-2.6%/+2.2%	-2.4%/+2.0%	-2.2%/+1.9%	-2.1%/+1.8%
92%	-7.2%/+4.5%	-4.7%/+3.4%	-3.7%/+2.8%	-3.1%/+2.5%	-2.7%/+2.2%	-2.5%/+2.0%	-2.3%/+1.9%	-2.1%/+1.8%	-2.0%/+1.7%
93%	-6.9%/+4.1%	-4.5%/+3.1%	-3.5%/+2.6%	-3.0%/+2.3%	-2.6%/+2.1%	-2.3%/+1.9%	-2.1%/+1.8%	-2.0%/+1.7%	-1.9%/+1.6%
94%	-6.6%/+3.8%	-4.2%/+2.9%	-3.3%/+2.4%	-2.8%/+2.1%	-2.5%/+1.9%	-2.2%/+1.8%	-2.0%/+1.6%	-1.9%/+1.5%	-1.8%/+1.5%
95%	-6.3%/+3.4%	-4.0%/+2.6%	-3.1%/+2.2%	-2.6%/+1.9%	-2.3%/+1.7%	-2.1%/+1.6%	-1.9%/+1.5%	-1.7%/+1.4%	-1.6%/+1.3%
96%	-5.9%/+2.9%	-3.7%/+2.3%	-2.9%/+1.9%	-2.4%/+1.7%	-2.1%/+1.5%	-1.9%/+1.4%	-1.7%/+1.3%	-1.6%/+1.2%	-1.5%/+1.2%
97%	-5.5%/+2.4%	-3.4%/+1.9%	-2.6%/+1.6%	-2.2%/+1.4%	-1.9%/+1.3%	-1.7%/+1.2%	-1.5%/+1.1%	-1.4%/+1.1%	-1.3%/+1.0%
98%	-5.0%/+1.8%	-3.0%/+1.5%	-2.3%/+1.3%	-1.9%/+1.1%	-1.6%/+1.0%	-1.5%/+1.0%	-1.3%/+0.9%	-1.2%/+0.9%	-1.1%/+0.8%
99%	-4.4%/+1.0%	-2.6%/+0.9%	-1.9%/+0.8%	-1.5%/+0.7%	-1.3%/+0.7%	-1.2%/+0.6%	-1.0%/+0.6%	-1.0%/+0.6%	-0.9%/+0.5%

Exact confidence interval based on the mathematical relationship between the F distribution and cumulative binomial distribution (Fleiss et al (2003)), Statistical Methods for Rate and Proportion, 3rd Edition

Table 2: 360-Day Complication Free Rate Estimated Values & 95.0% KM Conf. Inter. (Peto)

Estimated Value	Sample Size								
	100	200	300	400	500	600	700	800	900
70%	± 9.0%	± 6.4%	± 5.2%	± 4.5%	± 4.0%	± 3.7%	± 3.4%	± 3.2%	± 3.0%
71%	± 8.9%	± 6.3%	± 5.1%	± 4.4%	± 4.0%	± 3.6%	± 3.4%	± 3.1%	± 3.0%
72%	± 8.8%	± 6.2%	± 5.1%	± 4.4%	± 3.9%	± 3.6%	± 3.3%	± 3.1%	± 2.9%
73%	± 8.7%	± 6.2%	± 5.0%	± 4.4%	± 3.9%	± 3.6%	± 3.3%	± 3.1%	± 2.9%
74%	± 8.6%	± 6.1%	± 5.0%	± 4.3%	± 3.8%	± 3.5%	± 3.2%	± 3.0%	± 2.9%
75%	± 8.5%	± 6.0%	± 4.9%	± 4.2%	± 3.8%	± 3.5%	± 3.2%	± 3.0%	± 2.8%
76%	± 8.4%	± 5.9%	± 4.8%	± 4.2%	± 3.7%	± 3.4%	± 3.2%	± 3.0%	± 2.8%
77%	± 8.2%	± 5.8%	± 4.8%	± 4.1%	± 3.7%	± 3.4%	± 3.1%	± 2.9%	± 2.7%
78%	± 8.1%	± 5.7%	± 4.7%	± 4.1%	± 3.6%	± 3.3%	± 3.1%	± 2.9%	± 2.7%
79%	± 8.0%	± 5.6%	± 4.6%	± 4.0%	± 3.6%	± 3.3%	± 3.0%	± 2.8%	± 2.7%
80%	± 7.8%	± 5.5%	± 4.5%	± 3.9%	± 3.5%	± 3.2%	± 3.0%	± 2.8%	± 2.6%
81%	± 7.7%	± 5.4%	± 4.4%	± 3.8%	± 3.4%	± 3.1%	± 2.9%	± 2.7%	± 2.6%
82%	± 7.5%	± 5.3%	± 4.3%	± 3.8%	± 3.4%	± 3.1%	± 2.8%	± 2.7%	± 2.5%
83%	± 7.4%	± 5.2%	± 4.3%	± 3.7%	± 3.3%	± 3.0%	± 2.8%	± 2.6%	± 2.5%
84%	± 7.2%	± 5.1%	± 4.1%	± 3.6%	± 3.2%	± 2.9%	± 2.7%	± 2.5%	± 2.4%
85%	± 7.0%	± 4.9%	± 4.0%	± 3.5%	± 3.1%	± 2.9%	± 2.6%	± 2.5%	± 2.3%
86%	± 6.8%	± 4.8%	± 3.9%	± 3.4%	± 3.0%	± 2.8%	± 2.6%	± 2.4%	± 2.3%
87%	± 6.6%	± 4.7%	± 3.8%	± 3.3%	± 2.9%	± 2.7%	± 2.5%	± 2.3%	± 2.2%
88%	± 6.4%	± 4.5%	± 3.7%	± 3.2%	± 2.8%	± 2.6%	± 2.4%	± 2.3%	± 2.1%
89%	± 6.1%	± 4.3%	± 3.5%	± 3.1%	± 2.7%	± 2.5%	± 2.3%	± 2.2%	± 2.0%
90%	± 5.9%	± 4.2%	± 3.4%	± 2.9%	± 2.6%	± 2.4%	± 2.2%	± 2.1%	± 2.0%

Kaplan-Meier estimate confidence interval based on the Peto estimate of the standard error (Chemick, et al (2003)), Introductory Biostatistics for Health Sciences: Modern Applications Including Bootstrap. 1st Edition

5.7 Missing Data

Every effort will be utilized to minimize missing data. The number of data for each variable presented will be stated. The number of patients withdrawing from the Registry will be presented with their corresponding time of discontinuation. Time-to-event drop-outs will be censored, consistent with the Kaplan-Meier approach. Any data outside follow-up time period tolerance that was used for analysis will be noted with results presented.

5.8 Other Statistical Considerations

Confidence intervals and statistical tests if applied will be performed at a two-sided 5% significance level unless specified otherwise. All p-values will be rounded to three decimal places. If opportunities should arise, data mining and modelling analyses of the Registry database would be utilized for publication and/or medical conference presentation purposes as long as the integrity and objectives of the Registry are not compromised.

5.9 Retrospective Enrolment Minimal Dataset Requirements

The Registry protocol does allow for the retrospective enrolment of patients already implanted with a Boston Scientific S-ICD system. There are some specific criteria associated with these enrolments that must be fulfilled prior to the enrolment of a retrospective patient:

- The patient meets all the inclusion criteria and none of the exclusion criteria as listed in sections 6.1.1 and 6.1.2
- The patient must be a commercial patient, i.e. they have been implanted with the S-ICD system since the CE mark approval of the device (June 2009).
- The patient has been implanted with a device initially equipped with SW version 1.59.0 or later
- Details of all clinical events (including death as necessary) and all spontaneous episodes that received therapy since implant, are available in medical files or equivalent
- Details of all system related clinical events/hospitalizations and deaths since implant are available in medical files or equivalent

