5.3 Registry Endpoints

- **Registry Endpoint 1:** 30-Day S-ICD Complication-Free Rate*, will be summarized as the number of subjects and the percentages relative to the Registry population including the corresponding 95.0% two-sided exact binomial confidence interval.
- **Registry Endpoint 2:** 360-Day S-ICD Complication-Free Rate*, will be analyzed using the Kaplan-Meier (KM) estimate and its corresponding 95.0% confidence interval based on Peto estimate of the standard error.
- **Registry Endpoint 3:** The Percentage of Inappropriate Shocks for AF/SVT, will be analyzed by dividing the number of patients who received at least one inappropriate shock over the total number implanted patients. The mean, median and inter-quartile follow-up time will also be presented.

**Type I Complications will be considered to count towards the complication rate endpoints (see section 10.2). Events related to normal device function e.g. battery deletion within acceptable margins, will not count against the endpoints*

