6.1.1 Inclusion Criteria

Patients who meet all of the following criteria may be considered for inclusion:

- Eligible for implantation of an S-ICD system per local clinical guidelines or currently implanted with an S-ICD system (SW version 1.59.0 or later*)
- Willing and able to provide written informed consent or have informed consent as provided by a legal representative

**Patients currently implanted must meet minimal dataset requirements to be enrolled as described in Section 5.9*

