When programmed ON, the S-ICD System will deliver post-shock bradycardia pacing at a rate of 50 ppm for a maximum duration of 30 seconds. At the onset of post-shock sensing, a post-shock pacing escape interval is initiated. If one or more detections occur during this escape interval, post-shock pacing is deactivated. Once post-shock pacing is initiated, pacing is delivered in a demand mode and pacing will stop if an intrinsic rhythm is detected. The post-shock pacing waveform is a constant current, 200 mA, biphasic pulse with a pulse width of 7.5 ms per phase.

Induction of Arrhythmias for Device Testing

The pulse generator delivers an induction waveform when commanded by the S-ICD programmer. The 200 mA, 50 Hz AC induction waveform is delivered between the pulse generator and the subcutaneous electrode coil. The induction waveform is delivered until the induction button on the programmer is released. The programmer limits the induction waveform to a duration of 10 seconds. A subsequent induction waveform can be delivered by releasing the induction button and reselecting it once available.

Episode History

The pulse generator stores treated and non-sustained spontaneous episodes for subsequent retrieval using the programmer. The programmer displays the number of episodes, both spontaneous treated and non-sustained, as well as the number of delivered therapy shocks since the last follow-up. This data is automatically cleared when the programmer session is ended. An Episode Begin is declared at the onset of capacitor charging. Arrhythmias that terminate prior to the onset of capacitor charging are not retained. An Episode End is declared when the Tachycardia to NSR transition occurs following 24 intervals below the lowest programmer therapy zone.

An episode is considered treated when at least one shock has been delivered. Episodes are stored in a first-in-first-out format; however, the first stored treated episode is never overwritten.

An episode is considered non-sustained if capacitor charging occurs without the need to deliver any shocks. Non-sustained episodes are stored in a first-in-first-out format. All non-sustained spontaneous episodes have equal priority.

[figure not shown]
The EMBLEM MRI S-ICD stores additionally one atrial fibrillation (AF) episode for each day in which atrial fibrillation is detected. Up to seven of the most recent AF episodes can be stored.

Programmable Parameters

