- Rate of electrode failures and revisions, including the reason for revision
- Rate of device failures and revisions, including the reason for revision
- Rate of complications related to the S-ICD replacements
- Appropriate therapy for VT/VF
- Inappropriate shock therapy (e.g. atrial fibrillation, supraventricular tachycardia)

The following observational data will be collected and analysed additionally to the main study:

- Generator changes/electrode revisions
- VF induction testing at replacement
- Complications associated with S-ICD to TV-ICD change
- Additional invasive interventions (e.g. VT ablation)
- Use of anti-arrhythmic drugs
- Ventricular cycle length of episodes
- Duration (non-sustained episodes)

Patients enrolled in the Sub-Study must meet all inclusion criteria and none of the exclusion criteria as described below.

Inclusion Criteria

1. Subjects who are actively enrolled in the EFFORTLESS S-ICD Registry OR Subjects who completed the 5-year follow-up in the EFFORTLESS S-ICD Registry. All clinical events, spontaneous and induced episode data and system replacement or revision data since the last EFFORTLESS S-ICD Annual Follow-Up of the main study must be available in medical files or equivalent.
2. Subjects who are actively implanted with an S-ICD pulse generator (SQ-RX, EMBLEM or EMBLEM MRI) and an S-ICD electrode (Q-TRAK or EMBLEM) or any other future commercial available versions
3. Willing and able to provide written informed consent or have informed consent as provided by a legal representative and willing to participate in all testing and follow-ups as described the Sub-Study protocol
4. Age 18 or above, and of legal age to give informed consent specific to national laws

Exclusion Criteria

1. Subjects with device replacement from the S-ICD to a transvenous ICD
2. Subjects with unipolar pacemakers or implanted devices that revert to unipolar pacing
3. Subjects that are participating in any other investigational study that may interfere with interpretation of the Registry results, without the written approval of Boston Scientific

Once a patient is enrolled in the Sub-Study, the visit schedule according to Table 8 must be followed. Patients, who have still been actively enrolled in the main EFFORTLESS S-ICD Registry will be waived from the visit requirements as described in Table 3 (Section 7.1) and will be followed-up according to Table 8 only.

Table 8: Summary of information requested for the Sub-Study

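### Section 5.9 refuses retrospective patients whose known events or shocks lack full detail, so pooled shock and event rates may be biased, most plausibly low

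*Combined protocol and SAP*

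**What the plan says.** Section 5.9 sets "specific criteria associated with these enrolments that must be fulfilled prior to the enrolment of a retrospective patient". Two of these concern the outcome record:

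- One asks that particulars of every clinical event be on file and, likewise, that "all spontaneous episodes that received therapy since implant, are available in medical files or equivalent".
- The other overlaps with it and covers events tied to the system, hospital stays and deaths: "Details of all system related clinical events/hospitalizations and deaths since implant are available in medical files or equivalent".

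The footnote to Section 6.1.1 makes them part of eligibility, and Section 13.2 lists eligibility violations as one of only two reportable kinds of deviation. A site lacking the details of one treated episode must therefore refuse the patient or incur a deviation.

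No such condition applies to prospective patients. Sections 7.3.5, 7.4.1, 7.5.1 and 7.6 ask for follow-up data where available, and a missing episode report does not remove anyone. Section 5.0 analyses all enrolled patients, with no split by enrolment type. Section 5.7 deals with data missing after enrolment, not with patients refused because data were missing.

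Endpoint 3 (Section 5.3) is obtained by "dividing the number of patients who received at least one inappropriate shock over the total number implanted patients". Sub-Study inclusion criterion 1 (Appendix E) has a similar rule, covering "All clinical events, spontaneous and induced episode data and system replacement or revision data since the last EFFORTLESS S-ICD Annual Follow-Up".

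**The concern.** Entry depends on how complete the outcome record is, and the amount of record needed grows with the number of outcomes. A patient known to have had no event and no treated episode meets the two record conditions with nothing to produce. A patient known to have been shocked, but with one episode's details missing, does not. If such refusals happen more often among patients with events than among the rest, the retrospective cohort holds too few of them.

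The quantities exposed are Endpoint 3, the complication-free rates, time to first therapy, the linearised inappropriate-therapy rate and total shock burden. Section 2.0 says the Registry is meant to evaluate whether the S-ICD lowers complications and inappropriate therapy relative to transvenous systems, so a filter that plausibly favours the device matters. A larger sample does not remove it. Nor would approaching patients consecutively, which the documents ask for only in the Sub-Study.

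**Working it through.** **The plan's own figures.** The documents give no figure for this bias. Their precision figures reproduce:

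- 900 / (1 − 0.10) = 1000.
- Table 1 at 90%, n = 900: exact limits are −2.15 and +1.88 points, against −2.1/+1.9 printed.
- Table 2 at 90%, n = 900: 1.96 × 0.90 × √(0.10 / (900 × 0.90)) = 1.96 points, against ±2.0 printed.

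**Inputs to the illustration.** All are assumptions.

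- p, the true proportion of patients with an inappropriate shock: 10%. Section 1.2 reports close to this for any inappropriate therapy with transvenous devices.
- a, the chance that a shocked patient passes the record conditions, and r, the chance that any other patient does. Neither is given.
- f, the retrospective share of the cohort. Not given; 25% and 50% are used.

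**Formula.** Retrospective rate = p·a / (p·a + (1 − p)·r). This is below p only if a < r.

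**Case 1: everyone without an inappropriate shock passes (r = 1).**

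| Shocked patients refused | Retrospective rate | Pooled, f = 50% |
|---|---|---|
| 10% | 0.09 / 0.99 = 9.1% | 9.55% |
| 20% | 0.08 / 0.98 = 8.2% | 9.08% |
| 30% | 0.07 / 0.97 = 7.2% | 8.61% |

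**Case 2: other patients can fail too.** Section 5.9 covers all clinical events and all treated episodes, so appropriate shocks and events outside the endpoints also need details.

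- 20% of shocked and 10% of other patients refused: 0.08 / (0.08 + 0.81) = 9.0%.
- 5% of each refused: 10.0%, no bias.
- 5% of shocked and 10% of others refused: 0.095 / (0.095 + 0.81) = 10.5%, an upward bias.

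**Case 3: the burden grows with the number of episodes.** Let each treated episode be documented with probability q, so that a patient with k episodes passes with probability q^k. Keep r = 1.

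| q | k = 1 | k = 5 | k = 10 |
|---|---|---|---|
| 1.00 | 10.0% | 10.0% | 10.0% |
| 0.99 | 9.9% | 9.6% | 9.1% |
| 0.95 | 9.5% | 7.9% | 6.2% |

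At q = 0.95 and k = 5 the pooled rate is 9.5% if a quarter of the cohort is retrospective and 9.0% if half is.

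**Patient-level rate against shock totals.** Let the episode count among shocked patients be geometric with mean 3, and q = 0.95.

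- Pass probability: (0.95/3) / (1 − 0.95 × 2/3) = 0.864.
- Patient-level rate: 0.0864 / 0.9864 = 8.8%, a fall of 12%.
- Episodes per patient: 0.30 falls to 0.24, a fall of 20%.

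Totals lose more because patients with many episodes are the more likely to be refused.

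**The case against.** The strongest objection is that direction is not established. The bias is downward only if a < r, and the documents give neither. A site with an incomplete file may be unable to show that nothing happened, so patients without events can fail as well, and often-shocked patients may be seen and documented more closely. This stands as far as certainty goes. It does not make the two directions equally likely. If a general file check applies equally to everyone with pass probability r, a patient with K episodes must pass it and also have each episode's details, with probability r·q^K, which never exceeds r. An upward bias needs the other patients' files to be worse by enough to offset that.

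The device-memory argument is weak. Appendix A, Episode History, says "Episodes are stored in a first-in-first-out format; however, the first stored treated episode is never overwritten", which might suggest that heavily shocked patients lose records. But medical files are an accepted source, no storage capacity is given, the first treated episode is protected, and Endpoint 3 needs only one inappropriate shock per patient. Overwriting is at most a contributing possibility for shock counts and has no direct bearing on complications.

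The pooled shifts in case 1, 0.4 to 1.4 points, lie within the exact 95% interval for 10% at n = 900 (8.1% to 12.1%), and the Registry tests no hypothesis. That bears on importance; it does not excuse an avoidable bias. The Sub-Study version is also narrower: about 200 patients, with the record needed only from the last annual visit.

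Finally, retrospective patients must be "currently implanted with an S-ICD system (SW version 1.59.0 or later") and consent, which can leave out patients who died or were explanted before enrolment. That is a separate route to low rates and is not part of the arithmetic above.

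**Conclusion.** The concern holds in a limited form. Section 5.9 treats a known but incompletely documented event as grounds for refusal, prospective patients are not held to that standard, and no planned analysis would reveal the effect. Rates may be biased, most plausibly low, and more so for shock burden and linearised rates than for Endpoint 3.

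A reader might infer that event-free patients enter automatically, that heavily shocked patients are the likeliest to be refused, and that the retrospective rates are therefore biased low. The documents do not support that. Event-free patients still face the consent, implant-date, software and exclusion criteria. Refusal by number of shocks is an inference. The 9.1%, 8.2% and 7.2% figures assume that every patient without an inappropriate shock passes; relaxing that roughly halves the middle one's bias (9.0% instead of 8.2%) and can remove or reverse it. The retrospective share and the frequency of incomplete records are not stated, so neither size nor sign can be derived. This is a cheap improvement, not a demonstrated error in the results.

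**What to change.** - **Eligibility.** In Section 5.9, require that status since implant be known: any event and any shock (yes or no, with date), system status and vital status. Do not refuse a patient because details of a known event or episode are missing. Make the same change in Sub-Study inclusion criterion 1.
- **Coding.** Record such events with details unavailable and such shocks as rhythm unclassified. Report Endpoint 3 with unclassified shocks counted as not AF/SVT and again as AF/SVT.
- **Reporting.** Show Endpoints 1 to 3 separately for prospective and retrospective patients, with prospective-only as a sensitivity analysis, and report the number refused for incomplete records.

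The reporting is needed alongside the rule change, because that change still leaves out patients of unknown status and cannot recover those already refused.

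The cost is amendment wording in Section 5.9 and Appendix E, a CRF code, a count of refusals and a few extra tables. The downside is that some shocks cannot be adjudicated as Section 4.4 expects, so Endpoint 3 carries a lower and an upper value.

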Design:	
EFFORTLESS S-ICD is an observational, prospective, non-randomized Registry that will be conducted at approximately 50 clinical centres worldwide. Approximately 1000 patients implanted with, or meeting eligibility criteria for the implantation of the S-ICD system will be enrolled and followed per standard of care for up to 60 months post implant.
	
Primary Objective:	
To demonstrate the early, mid- and long-term clinical outcome of the S-ICD system.
	
Registry Endpoints	
 • Perioperative (30 days post implant) Complication-Free Rate • 360-day Complication-Free Rate • Percentage of Inappropriate Shocks for AF/SVT 	
Observational Data Collection	
 • Clinical Indications for implant • Patient demographics • Type of anesthesia/analgesia • Implant procedure duration • Use of fluoroscopy and X-Ray • Shock conversion efficacies (spontaneous & induced) • All cause therapies (appropriate & inappropriate) 	
 • Overall complication rates with time • Frequency of scheduled/unscheduled follow-ups/hospitalizations • All cause mortality • Length of hospital stay (implant procedure and follow-ups) • All clinical events • Clinical event rates over time • Quality of Life

	
 Total shock burden 	
 Hospital personnel implant and follow-up experience (using surveys)
Sample Size:	The target sample size is approximately 1000 patients.	
Registry Duration:	The expected duration, from enrolment to closure of the main Registry, will be approximately 108 months.	
Patient Selection:	Patients from the investigators' general implantable cardioverter-defibrillator (ICD) patient population will be eligible to be enrolled in this Registry. Patients should meet all the inclusion criteria and none of the exclusion criteria. Retrospective enrolments are allowed providing minimal data requirements are met.	

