3.2.1 Observational Data Collection

When available, descriptive statistics will be used to present observational data to further characterize the performance of the S-ICD system. This can include (but is not limited to):

- Clinical Indications for implant
- Patient demographics
- Type of anesthesia/analgesia
 - General anesthesia/local anesthesia/conscious sedation etc.
- Implant procedure duration
- Use of fluoroscopy and X-Ray
- Induced Shock Conversion Efficacy
 - Defined as any shock delivered by the S-ICD pulse generator that terminates the induced arrhythmia and does not require an external defibrillator.
- Spontaneous Shock Conversion Efficacy
 - Defined as any shock delivered by the S-ICD pulse generator that terminates the spontaneous arrhythmia (device defined end of episode)
- First Shock Conversion Efficacy
 - Defined as the percentage of successful conversions (device defined end of episode) caused by the first shock delivered by the S-ICD pulse generator. Data will be evaluated for both induced and spontaneous episodes
- All cause therapy (appropriate and inappropriate)
 - Inappropriate therapy is defined as delivery of shock therapy for any rhythm other than VT/VF.
- Total Shock Burden
 - Defined as the total number of therapies delivered (both appropriate and inappropriate) divided by the total number implanted patients
- Complication rates over time
- Frequency of scheduled and unscheduled follow-ups/hospitalizations
- All cause mortality
- Length of hospital stay
 - Where possible, hospital stay lengths will be calculated for implant procedure as well as scheduled and unscheduled follow-ups

- All clinical events
- Clinical event rates over time
- QOL Assessments
 - Patients will complete a brief set of standardized QOL questionnaires at baseline (pre-implant), 3 months post-implant, 6 months post-implant and 12-months post implant (see section 7.8) with the intention of comparing scores with a transvenous ICD cohort
- Hospital personnel implant and Follow-Up Experience (using an optional survey to be completed at two time points)

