7.2 Enrolment

Patients may not be enrolled in the Registry until the investigator receives “Approval to Enrol” from the sponsor. Patients are considered enrolled after providing written informed consent in accordance with applicable local and national guidelines and/or Ethics Committee (EC) requirements.

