12.3 Informed Consent

Unless otherwise dictated by local or National guidelines governing the study, written informed consent is required from all patients or their legal representative, prior to participation in this Registry. The Sponsor/ or Sponsor's representative will provide a template informed consent document in local language. For centres where EC approval is required, the informed consent should also be approved. In the event no EC approval is required, the final version of the informed consent will be agreed between the Sponsor/ or Sponsor's representative and the investigational centre. Significant changes to the consent document provided by the Sponsor may need to be reviewed and approved by Boston Scientific before a patient provides written informed consent.

If new information becomes available that can significantly affect a patient's future health and medical care, that information shall be provided to the patient(s) affected in written form. If relevant, all affected patients shall be asked to confirm their continuing informed consent in writing.

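### Section 5.9 allows for deaths before a retrospective enrolment, but 6.1.1 and 7.2 give no route for a deceased patient to enter; to the extent such patients are missing, mortality from implant is biased low, and the complication-free rates may be overstated

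*Combined protocol and SAP*

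**What the plan says.** The synopsis (Patient Selection) permits entry after implant: "Retrospective enrolments are allowed providing minimal data requirements are met". It sets no cap on the share of such patients. Section 5.9 reaches back to the CE mark in June 2009 and sets no maximum interval between implant and consent.

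Two conditions in 5.9 mention death before enrolment: "Details of all clinical events (including death as necessary) and all spontaneous episodes that received therapy since implant, are available" and "Details of all system related clinical events/hospitalizations and deaths since implant are available in medical files or equivalent".

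Another condition in the same list is "The patient meets all the inclusion criteria and none of the exclusion criteria as listed in sections 6.1.1 and 6.1.2". Section 6.1.1 admits a patient who is eligible for an implant or currently implanted, and who is "Willing and able to provide written informed consent or have informed consent as provided by a legal representative". Section 7.2 fixes the moment of entry: "Patients are considered enrolled after providing written informed consent". Section 12.3 has a qualifier: "Unless otherwise dictated by local or National guidelines governing the study, written informed consent is required from all patients".

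On analysis, section 5.0 includes everyone enrolled. Section 5.5 gives 30-day percentages and long-term linear or Kaplan-Meier rates for clinical events, and section 5.7 censors drop-outs. Sections 4.1, 4.3 and 7.5 count follow-up from implant. "All cause mortality" is listed in 3.2.1 as an observational item.

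**The concern.** A retrospective patient who had to be alive to consent brings in follow-up, from implant to consent, during which no death could have been recorded. If that time counts in the Kaplan-Meier risk set or in the patient-year denominator, mortality from implant comes out too low. The amount depends on how many patients were enrolled late and how late, not on the device or the patients. The plan has no delayed entry, no analysis restricted to patients consented before implant, and no split by enrolment type for mortality.

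The same rule bears on complications. A patient whose system was fully explanted for a complication before consent is no longer currently implanted, and 5.9 makes no exception. Complications that left the patient with an S-ICD can still be captured from the records. Those that ended in full explant can be lost, and they count against Endpoints 1 and 2 if they are Type I.

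The Registry's objective is early, mid- and long-term clinical outcome. The planned confidence intervals do not reflect this kind of error.

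**Working it through.** **The texts side by side.** Section 5.9 treats death before enrolment as possible. Sections 5.9 (through 6.1.1) and 7.2 require a currently implanted patient and written consent. There are three possible openings for a deceased patient:

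- Legal-representative consent in 6.1.1, which does not say that it extends to a patient who has died.
- The local-guideline qualifier in 12.3, which does not mention deceased patients. Section 13.2 lists unavailable consent as a deviation.
- The Deaths tick in the Enrolment column of Table 3, which may mean only deaths after consent and before implant.

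None of these states a route.

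**Inputs.** The plan has no mortality figure to reproduce, and it gives no mortality rate, retrospective share or lag. All three are therefore assumptions: annual mortality m = 2-6%, retrospective share f = 10-50%, implant-to-consent lag L = 0.5-2 years. The hazard is taken as constant, and no patient who died before consent is entered.

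**Formulas.**

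- True mortality by year t: F(t) = 1 - (1-m)^t.
- Retrospective patients, who must survive the lag: 0 for t ≤ L, and F(t-L) after that.
- Pooled estimate under the plan: (1-f)·F(t) + f·F(t-L).

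**Worked case: m = 4%, f = 25%, L = 1 year.**

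- 1 year: true 4.00%; pooled 0.75 × 4.00 + 0.25 × 0 = 3.00%.
- 5 years: true 1 - 0.96^5 = 18.46%; retrospective 1 - 0.96^4 = 15.07%; pooled 0.75 × 18.46 + 0.25 × 15.07 = 17.61%.
- Linear rate over 5 years: true 4.08 and pooled 3.86 per 100 patient-years.

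**Range.** The shortfall is (true - pooled)/true.

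| m, f, L | 1-year true / pooled | Shortfall | 5-year true / pooled | Shortfall |
|---|---|---|---|---|
| 2%, 10%, 0.5 y | 2.00 / 1.90 | 5% | 9.61 / 9.52 | 0.9% |
| 6%, 10%, 0.5 y | 6.00 / 5.70 | 5% | 26.61 / 26.38 | 0.9% |
| 4%, 25%, 1 y | 4.00 / 3.00 | 25% | 18.46 / 17.61 | 4.6% |
| 6%, 50%, 2 y | 6.00 / 3.00 | 50% | 26.61 / 21.78 | 18% |
| 2%, 50%, 2 y | 2.00 / 1.00 | 50% | 9.61 / 7.74 | 19% |

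Once the lag reaches the reporting time, the pooled figure is (1-f) times the true one, so the relative shortfall equals f whatever the mortality rate.

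**Does delayed entry repair it?** In a simulation of the worked case (400,000 patients), Kaplan-Meier with retrospective patients entering the risk set at consent gave 3.97% at 1 year and 18.48% at 5 years, against true values of 4.00% and 18.46%. Ignoring the entry time gave 2.98% and 17.64%.

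The effect on Endpoints 1 and 2 was not quantified, because the documents give nothing on explants before consent.

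**The case against.** The strongest reply is that the premise is not established. The three openings above might let some deceased patients in, and each one entered shrinks the immortal time. That stands: the documents show an unreconciled rule, not proof that nobody enters after death. A reader might infer that such deaths are shut out at most sites, or that entry differs by national consent practice. The documents describe no site or country practice, and 12.3 says nothing about the deceased, so neither inference is supported.

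Second, all-cause mortality is descriptive, is not one of the three Registry endpoints, and has no method of its own. A 1-year or 5-year mortality from implant is a natural reading of 5.5 but is not spelled out. This limits how much weight the point carries. It does not remove the bias, because each form of rate in 5.5 is affected when time runs from implant.

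Third, a reader might infer that reported mortality would be half the true value. That follows only from assuming a 50% retrospective share and a lag of at least a year; at other shares the shortfall changes with the share. At 5 years the worked-case shift is 18.46 - 17.61 = 0.85 points, less than a 95% half-width at n = 900 of 1.96 × √(0.1846 × 0.8154/900) = 2.5 points. That is a fair comment on size, but more patients would not reduce the bias.

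**Conclusion.** The point holds in conditional form. Section 5.9 and sections 6.1.1 and 7.2 are not reconciled on patients who died before consent. To the extent that these patients are not entered, pooling everyone from implant with right censoring only biases all-cause mortality downward. Under the assumed ranges the relative shortfall is about 5-50% at 1 year and about 1-19% at 5 years, largest when the retrospective share is high and the lag long. These figures assume a constant hazard and no entry after death; they shrink as more such patients are entered. The true size cannot be derived from the documents.

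It would be wrong to confine the point to mortality. The requirement to be currently implanted can also remove patients fully explanted for a complication, so Endpoints 1 and 2 may be overstated by an unknown amount. Nothing in the documents shows that they are.

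**What to change.** 1. **Sections 5.9, 6.1.1 and 7.2:** state whether patients who died or were fully explanted before consent may be enrolled and, if so, by what consent route.
2. **Section 5.5, all-cause mortality:** keep time since implant as the scale, but let retrospective patients enter the risk set at their consent date. Patient-years for linear rates should start there too. List any patients entered after death by site and leave them out of this analysis, since they have no time at risk after consent. This assumes that, among survivors, the timing of consent is unrelated to the risk of death.
3. **Sections 5.3 and 5.5:** also report mortality and Endpoints 1 and 2 in patients consented before implant. Delayed entry for mortality does not recover explanted patients, so this cohort is the check for the complication endpoints.
4. Report the retrospective share and the distribution of the implant-to-consent lag.

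The cost is a few sentences, fewer patients at risk early in the mortality curve with wider intervals there, and possibly less favourable figures. The consent date must be in the main Registry database. Its collection is explicit only for the Sub-Study (Appendix E); Table 4 lists the main consent form as retained at the centre.
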